**Figure 1. Schematic Diagram of Study Design**

Throughout the study, subjects will be monitored carefully for occurrences of adverse events, laboratory test abnormalities, and changes in vital signs. The expected duration of each subject's participation in this proposed clinical investigation is approximately 8 months. For the REDS-III RBC-OMICs subgroup, the subject's participation is approximately 12 months.

Samples of the various subgroups will be analyzed for storage and stress-induced hemolysis, membrane microvesicle formation and for sickle cell trait (AS), and SNPs in ANK1, G6PD, PIEZO1, SPTA, ESYT2, Myo9b, and SEC14. And/or we identify additional non-synonymous SNPs that are associated with susceptibility to hemolysis of stored red blood cells. We may identify additional SNPs as our analysis of the REDS-III GWAS study advances that could replace one of these SNP groups. These findings will be compared with SNPs from the sample analyses of the REDS-III GWAS study. The analysis will occur in the labs of [name] in the Vascular Medicine Institute by qualified study personnel.

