Monitoring of safety and data quality in the proposed study will be the responsibility of all personnel on the project, with primary responsibility and supervision by the Investigator. The Institutional Review Board will approve the Statement of Informed Consent for the study and provide institutional oversight of data and safety issues. The study protocol will be approved prior to recruiting or obtaining consent from any participants. Moreover, the study will be reviewed at a minimum of annual basis (or more frequently as deemed necessary) by the IRB committee. Each participant will sign the Informed Consent Form described above prior to participating in the study. To ensure participant safety, once participants are enrolled in the study, study staff will immediately report all adverse and serious adverse events to one of the Investigators. The Investigator will, per standardized procedures, report them to the IRB for their review. These events should also be communicated to the sponsor of the IND. With regard to monitoring of data quality and protected health information, all required personnel proposed for this project will have the required human subjects and confidentiality training, which includes information about maintaining data integrity and security. Confidentiality will be guarded using established procedures such as storing data in locked cabinets within locked offices or locked data rooms,

coding by study identification numbers rather than any personally identifying information to avoid revealing the identity of subjects, and aggregating data across participants. The key linking names and study identification numbers will be kept separately from the data sets with limited access by study personnel. However, Vitalant staff members and the HSCLab staff members will need to have the study ID number on documents with the subjects name to add to the level of protection when identifying the subject's blood unit and in order for the blood to be released. Only study personnel will have access to the data sets on protected servers. Oversight of all aspects of data management will occur with the Investigator. Subject's de-identified biological samples and data will be stored for future research analyses and may be shared with other researchers', their laboratories or federal repositories.

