Only the REDS-III RBC-OMICS subject's de-identified biological samples and data may contain the subject's SNP and will be stored for future research analyses and may be shared with other researchers', their laboratories or federal repositories. The subject's de-identified biological samples and data may contain the subject's SNP for the biotin study team to know which SNP subgroup the subject is in. Three of the analyses that may be done at Wake Forest University, Yale University, and Vitalant.

The future analysis could include genetic analyses, including whole genome sequencing.

Data Monitoring Plan. The proposed study will use the FDA definition of adverse events (AE) and serious adverse events (SAE). Any SAE, which is unexpected and related to study intervention, will be reported immediately to the IRB and will be followed by an additional letter detailing the nature of the SAE. In the event that a participant either withdraws from the study or the investigators decide to discontinue a participant due to a SAE, the participant will be monitored by the co-PIs until (a) a resolution is reached (e.g., the problem has resolved or stabilized with no further change expected), (b) the SAE is determined to be clearly unrelated to the study intervention, or (c) the SAE results in death. Outcomes of SAEs will be regularly reported to the IRB and the sponsor. A summary of the SAEs that occurred during the previous year will be included in the annual progress report as well as in the annual IRB renewal.

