#### **6.4.3 Parameters to be monitored**

The following progress will be monitored throughout the course of the research to ensure the safety of subjects as well as the integrity and confidentiality of their data.

- An evaluation of the progress of the research study, including subject recruitment and retention, and an assessment of the timeliness and quality of the data.
- A review of collected data (including adverse events, unanticipated problems, and subject withdrawals) to determine whether there is a change to the anticipated benefit-to-risk assessment of study participation and whether the study should continue as originally designed, should be changed, or should be terminated.
- An assessment of external factors or relevant information (eg. pertinent scientific literature reports or therapeutic development, results of related studies) that may have an impact on the safety and study participants or the ethics of the research study.
- A review of study procedures designed to protect the privacy of the research subjects and the confidentiality of their research data.

The severity of adverse changes in physical signs or symptoms will be classified as follows:

- Grade 1 (Mild): asymptomatic or mild symptoms; clinical or diagnostic observation only; intervention not indicated.
- Grade 2 (Moderate): minimal, local or noninvasive intervention indicated; limiting age-appropriate ADL (Activities of Daily Living).
- Grade 3 (Severe): medically significant but not immediately life-threatening; hospitalization or prolongation of hospitalization indicated; disabling; limiting self care ADL.
- Grade 4 (Life-threatening): consequences; urgent intervention indicated.
- Grade 5 (Death): event is a direct cause of death.

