#### **6.4.5 Reportable Adverse Events**

For this study, a serious adverse event is any untoward clinical event that is thought by either the investigator or the sponsor to be related to the study and results in any of the following outcomes: that is also:

- 1) Death
- 2) A life threatening adverse event
- 3) Inpatient hospitalization or prolongation of an existing hospitalization
- 4) A persistent or significant incapacity or substantial disruption of the ability to conduct normal life functions
- 5) A congenital anomaly or birth defect
- 6) Important medical events that may not result in death, be life threatening, or require
- 7) hospitalization may be considered serious when, based upon appropriate medical judgment, they may jeopardize the patient, or subject, and may require medical, or surgical intervention to prevent one of the serious outcomes listed above.

If clinically important and unexpected adverse experiences or clinically important study-related adverse experiences occur, they will be recorded on the adverse event case report form.

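### Section 6.4.5 states a narrower rule for the adverse event form than sections 6.4.2, 6.4.3 and 6.5.1 imply; the passages should be reconciled so that every adverse event is recorded

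*Combined protocol and SAP*

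**What the plan says.** Section 6.4.5 of the combined protocol and SAP, after its list of serious outcomes, says: "If clinically important and unexpected adverse experiences or clinically important study-related adverse experiences occur, they will be recorded on the adverse event" case report form. It does not define clinical importance. No other section says what goes on the adverse event form.

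Other sections speak of adverse events without a threshold:

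- Section 2.2.1, in the text with Figure 1: throughout the study "subjects will be monitored carefully for occurrences of adverse events, laboratory test abnormalities, and changes in vital signs".
- Section 6.4.2: "study staff will immediately report all adverse and serious adverse events to one of the Investigators". The same section adopts the FDA definition of an adverse event and states no importance filter.
- Section 6.4.3: the severity scale has five grades and begins with "Grade 1 (Mild): asymptomatic or mild symptoms; clinical or diagnostic observation only; intervention not indicated".
- Section 6.5.1: all of a subject's demographic and clinical information is to be kept on a case report form.
- Section 2.2.2 and Appendix A: an adverse event assessment is scheduled at the RBC-OMICs visit and at Visits 3 to 10 of the infusion study.

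**The concern.** Collection, grading and onward reporting are written for all adverse events, but the recording rule is written for a subset. The subset depends on three judgements by the investigator: importance, expectedness and relatedness. The first of these has no definition, so two investigators could fill in the form differently for the same mild rash and both be following the text.

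Section 2.5.4 says that data are first written on paper forms at the visit and then entered in a database whose screens mirror those forms. An event kept off the adverse event form therefore has no stated route into the adverse event part of the database. Section 6.1 names fever, chills, itching, rash and hives among the known reactions to transfusion. Mild cases of these are the events most exposed to the filter. The subjects are healthy volunteers with no direct benefit (section 6.3), so a complete account of minor reactions is a reasonable thing to expect. An event not written down at the visit may be hard to recover later.

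The point concerns entry of events on the form. It does not concern the definition of a serious adverse event in the same section.

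**Working it through.** The plan states no adverse event rate, safety endpoint or adverse event table (sections 2.4 and 2.5), so there is no figure to reproduce. The check is mainly a reading of the rule.

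**Step 1: what 6.4.5 admits.** An event is entered if it is (important and unexpected) or (important and related). With three yes/no judgements there are eight combinations.

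| Clinically important | Expected | Judged related | Entered under 6.4.5 |
|---|---|---|---|
| yes | no | yes | yes |
| yes | no | no | yes |
| yes | yes | yes | yes |
| yes | yes | no | no |
| no | any | any | no (four combinations) |

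Three combinations are entered and five are not. Expectedness alone does not exclude an event: an important, study-related reaction is entered even if it was expected. What falls outside is every event judged not important, plus the important event that is both expected and judged unrelated.

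**Step 2: compare with the other sections.** Sections 6.4.2 and 6.4.3 draw no line at any of the five excluded combinations. The lowest grade, which needs no intervention, has little use on a form limited to important events. The general statement in 6.5.1, if it covers adverse events, cannot be met on the adverse event form as 6.4.5 describes it.

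**Step 3: where the data go.** Section 6.4.3 lists among the matters to be monitored: "A review of collected data (including adverse events, unanticipated problems, and subject withdrawals) to determine whether there is a change to the anticipated benefit-to-risk assessment". Section 6.4.2 gives the DSMB accumulated and summary safety data. Neither section says whether those data come from the adverse event form. The effect on oversight therefore depends on an unstated source.

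**Step 4: illustration under assumed values.** Let p be the true share of subjects with any adverse event and s the share of those whose event meets the 6.4.5 threshold. The rate on the form is then p × s. Neither p nor s is in the documents. Take n = 70, the evaluable infusion target in section 2.5.1.

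- p = 20%, s = 75%, 50% or 25%: the form shows 15%, 10% or 5%, that is 10.5, 7 or 3.5 subjects, where 70 × 0.20 = 14 had an event.
- p = 5%, s = 25%: the form shows 0.05 × 0.25 = 1.25%, or 70 × 0.0125 = 0.9 subjects, where 70 × 0.05 = 3.5 had an event. The chance that the form shows at least one falls from 1 − 0.95^70 = 97% to 1 − 0.9875^70 = 59%.

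Section 2.5.1 also foresees approximately 90 completers once the 20 subjects with SNPs are added. The ratio s is unaffected and the counts scale by 90/70. Because s cannot exceed 1, a rate taken from the form alone can only be equal to or below the true one.

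**The case against.** The strongest reply is that 6.4.5 says certain events will be recorded and does not say that others will not. That is literally so. But the qualifiers would serve no purpose on a form that takes everything, so restriction remains the natural reading.

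A reader might infer that mild and expected reactions are lost. The documents do not support that.

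- Important, related reactions are entered even when expected.
- All adverse events reach an Investigator, and under 6.4.2 "The Investigator will, per standardized procedures, report them to the IRB for their review", with communication to the IND sponsor as well.
- Section 6.4.4 has the team meet about monthly and review how adverse events are identified and documented.
- Section 6.5.1 puts all clinical information on a case report form.

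Events missing from the adverse event form may therefore exist elsewhere.

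Nor can one say that a Grade 1 event is never entered. An asymptomatic anti-BioRBC antibody could well be judged important and related: section 2.3.3 calls antibody formation the primary safety concern, and section 6.4.8 makes it a ground for withdrawal.

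It is also fair to object that no planned safety rate exists to be biased, and that sections 6.4.2 and 6.4.3 never name the form as the DSMB's source. Both objections stand, and they make the consequence conditional. The conflict between the recording rule and the other sections remains.

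**Conclusion.** The point holds as an inconsistency in the recording rule with a conditional effect on safety data. Section 6.4.5 filters entry on the adverse event form by an undefined notion of clinical importance, combined with unexpectedness or relatedness. Sections 6.4.2, 6.4.3 and 6.5.1 carry no such filter.

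Under-counting follows on two assumptions: that staff apply 6.4.5 in its natural, restrictive sense, and that the form is the source for safety summaries or DSMB review. The direction is then downward for events judged not important and for important events that are both expected and judged unrelated. The documents give no basis for the size; the figures above are illustrations.

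Two stronger conclusions are tempting. The first is that the trial's safety rates will be too low; the plan defines none. The second is that the DSMB will see a filtered list; the plan does not say where its data come from. A version that supposes 5-10% of subjects with a mild reaction and then a report of 0 of 90 needs an assumed rate, every reaction judged unimportant, and no other record used. The documents establish none of these.

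No efficacy endpoint is affected. The correction is still worth making, because events not recorded at the visit may not be recoverable.

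**What to change.** Replace the sentence in 6.4.5 with: *All adverse events, whatever their severity, expectedness or relatedness, will be recorded on the adverse event case report form with grade (6.4.3), expectedness and relatedness.* This brings 6.4.5 into line with 6.4.2, 6.4.3 and 6.5.1. It also lets any later summary be restricted by importance or relatedness at the analysis stage, where the choice is visible.

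Leave the expedited-reporting criteria in 6.4.6 as they stand. They rest on fatal or life-threatening outcome, seriousness, unexpectedness and association with the study drug or procedures. They do not use clinical importance, and that undefined term should not be carried into them.

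The cost is one sentence and some extra form entries. The adverse event assessments are already scheduled and the grading scale already exists.

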#### **6.4.6 Adverse Events Reporting Timeline**

Life-threatening or fatal unexpected adverse events associated with the use of the study drug or procedures must be reported to the IRB within 24 hours of discovery of the incident with subsequent follow-up submission of a detailed written report.

The FDA will be notified by telephone or facsimile transmission of a human adverse event that is fatal or life-threatening no later than 7 calendar days after receiving the respective human adverse event information, followed by the subsequent submission of a written IND Safety Report.

Serious and unexpected adverse events associated with the use of the study drug or procedures will be reported to the IRB with subsequent follow-up submission of a detailed written report in accordance with the respective policies and procedures of the IRB. Written IND Safety Reports will be submitted to the FDA as soon as possible and, in no event, later than 15 calendar days following the investigator-sponsor's receipt of the respective adverse event information.

A summary report of the findings will be prepared and submitted to the regulatory agencies.

The unexpected, life-threatening or fatal, suspected adverse reaction will be reported to the NHLBI within 7 calendar days. Unanticipated problems suggesting greater risk of harm to study participants than was previously known or recognized will be reported to NHLBI within 30 calendar days. Expedited SAE/UP reports to NHLBI will include the following elements:

- Study title, grant/contract number, PI name
- Description and date of the event or problem, including why it merits expedited reporting
- When available, date(s) when the event was reported to applicable governing bodies (e.g., IRB, FDA)
- Any corrective action planned or taken in response to the event or problem (e.g., study suspension, consent or protocol changes, additional training or security measures)

Communications from other applicable oversight bodies (eg: IRB, FDA, iDSMB) regarding any applicable SAE/UP will also be reported to NHLBI.

#### **6.4.7 Reporting of Changes to Protocol and Consent**

Any change in research procedures that would result in an increased risk to human subjects will be submitted to the IRB for review and approval prior to implementation of the changes in study practice. In the event that the study is suspended or terminated by the IRB or by the DSMB, or for other reasons, the NHLBI will be notified in writing including details as to the reasons for suspension or termination and any recommendations made by the IRB or DSMB. The FDA will also be notified of any changes to the protocol, suspensions or termination.

#### **6.4.8. Withdrawal of Subjects and Stopping Criteria:**

##### **STOPPING RULES:**

**Withdrawal of Subjects:** Subjects must be withdrawn from the study for the following reasons:

- An SAE or a serious post-infusion hemolytic event that is determined to be possibly, probably, or definitely related to the infusion of autologous BioRBC.
- Detection of anti-BioRBC antibodies following first infusion. In the unlikely event that a study subject tests positive for bioRBCs following first infusion, the subject will be withdrawn from

the study. The subject will not receive the subsequent RBC infusion. Since anti-BioRBC antibodies attack BioRBCs, the 2-4 hours post transfusion survival and mean lifespan measurements will be affected. Based on the time of discovery, the 2-4 hours time point measurement may be retained or discarded. The participant will be followed for signs and symptoms of hemolysis as well as the disappearance of the anti-biotinylated RBC antibodies.

Subjects may be withdrawn from the study for the following reasons:

- In the unlikely event that a stored unit does not pass the endotoxemia test, red blood cells will not be transfused and will have to be withdrawn from the study.
- In the event that a donated RBC unit is misplaced, the subject's participation in the study will be terminated since an autologous transfusion will no longer be possible.
- At their own request
- At the specific request of the Investigator (eg detection of a new significant safety concern related to the study drug).
- Occurrence of intercurrent diseases which in investigator's opinion, continuation of the study drug would be harmful to the subject's well-being.
- Pertinent non-compliance with the conditions for the trial or instructions by the investigator.
- Lost to follow up

Any subject removed from the study will remain under medical supervision until the condition is medically acceptable. Study subjects removed from the study will be replaced by enrolling another volunteer with similar demographic

**Discontinuation of the Clinical Trial:** RBC transfusion is a common clinical procedure. As such, this is a minimal risk clinical study that poses little to no risk to the study subjects, especially since the RBCs to be transfused are autologous. Other than the adverse events described above and those listed in the exclusion criteria, we do not currently anticipate any sources of issues that will discontinue the clinical trial. However, for safety reasons, we will discontinue the study if any of the subjects enrolled experience any unexpected fatal or life-threatening events that can be attributed to the biotinylated autologous RBCs; the study will be halted until data review by investigators and the iDSMB has rendered a final recommendation about study continuation.

## 6.5 RISK MANAGEMENT PROCEDURES

### 6.5.1 Protection Against Risks

#### General Risks of Study Protocol and Procedures

- All research interventions/activities will be conducted in private patient care areas. The collection of sensitive information about subjects is limited to the amount necessary to achieve the aims of the research, so that no unneeded sensitive information is being collected.
- All demographic and clinical information about the subject will be stored on a Case Report Form which will be completed for each subject enrolled into the clinical study. A relational database will be constructed on a local server with daily backups where only select research team members will have access to the database. The electronic data capture system being used for this clinical research study has not been fully certified as being compliant with the FDA regulations at 21 CFR Part 11 due to the limited scope of this clinical research study. Data will be entered on the server over an encrypted network connection, and stored behind

a secure firewall. The case report forms with study IDs will be housed in the same chart as personal identifier documents are while the subject is active in the protocol. Personal information documents will be stored separately once each subject's participation is complete. Only limited team members will have access to charts and database. Other data quality assurance measures will include verifying the data, out of range data checks, and repeated evaluation of the data process. All members of the research team should receive appropriate training about securing and safeguarding research data.

- Specimens will be stripped of subject identifiers and stored according to a similar coding protocol as described above. These specimens will be stored safely in the custody of the Investigator responsible for the individual assays. The Investigators will limit future access to any remaining sample to only those investigators with prior IRB approval for their studies.
- All staff involved in this study are properly credentialed and instructed in the areas of testing, confidentiality, and safety.
- The Investigator will retain the data for the entire period of this study and will retain the specified records and reports until two years after investigations under the IND have been discontinued and the FDA is notified. The Investigator may continue to use and disclose subjects' de-identified information for the purpose of this study for a minimum of seven years after final reporting or publication of the study. If the subject and/or legal representative decide to withdraw or be withdrawn from study participation, they may request that the study data and samples be destroyed. Subject names or other directly identifiable information will not appear on any reports, publications, or other disclosures of clinical study outcomes.

